6. PROCEDURES

Study Design. A randomized, placebo-controlled, double blind, parallel group clinical trial will be conducted to assess the efficacy of 12-weeks of oral nicotinamide riboside capsules (NR; 500mg, 2x/day, trade name NIAGEN®, ChromaDex Inc., Irvine CA) for improving memory and other cognitive functions in adults with cognitive scores indicative of aMCI. Secondary outcomes will include measures of vascular/cerebrovascular and neuronal function and brain structure. This design and duration has been used previously to study the efficacy of interventions for improving vascular function in older adults⁷. Study participants and investigators involved in data acquisition and/or analysis will be blinded to treatment condition. All primary and secondary outcome measures will be made at baseline and after 12 weeks of treatment. Visits will take place in the Neurovascular Aging Laboratory (NOVA Lab) on the STAR Research Campus at the University of Delaware, with the exception of MRI measures which will be made at the UD Center for Biomedical Brain Imaging (CBBI). Details pertaining to the safety and toxicity of the intervention and rationale for the proposed frequency and duration are presented at the end of this section.

DETAILED OVERVIEW OF STUDY VISITS

PRE-SCREENING PHONE SCREENING

Prior to scheduling Visit 1 informed consent & screening, a member of the research team will complete a brief phone screen and will ask the subject the COVID-19 questionnaire in order to ascertain specific information regarding possible hospitalization as a result of COVID-19 diagnoses, and vaccination. If subject acknowledges any hospitalization as a result of COVID-19, the subject will be excluded and will not be permitted to enroll in the current study. If the subject discloses specific information as it relates to receiving the COVID-19 vaccine, the subject will not be permitted to participate in any data collection procedures until one week following any COVID-19 vaccination. These questions will also be asked during the week 10 phone check-in before scheduling week 12 visits.

VISIT 1: INFORMED CONSENT & SCREENING (2.0 hours)

Subjects will be instructed to fast for \geq 12 hours before testing

Informed Consent for participation in the clinical trial will be obtained by a trained member of the

	Week	Visit #	Duration	Location	Visit Description	Blood

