- **Total Cerebral Blood Flow** (CBF) will be assessed using extracranial high-resolution duplex ultrasound to capture both diameter and time-averaged MFV of the bilateral internal carotid arteries (ICA) and vertebral (VA) arteries (i.e., the two primary arteries that supply the brain)^{11–13}. CBF will be calculated for each artery as follows: CBF = MFV x π (diameter/2)² and summed in order to estimate total cerebral blood flow¹².
- **Neurovascular Coupling** will be assessed by measuring the Δ MFV_{MCA} and Δ MFV_{PCA} from 0 baseline in response to the progressively difficult N-back mental task of executive function and a repetitive visual stimulus^{14–16}. MFV_{MCA} and Δ MFV_{PCA} will be collected using TCD ultrasonography as described above. The N-back Cognitive Test measures working memory and executive function and activates areas of the brain supplied by the MCA. A computer program will display a series of numbers and the subject will be required to respond by clicking a button when the current number is identical to the same number N-trials previously. A control (0-back) level and two N-back levels will be performed. Numbers will be displayed with an inter-stimulus duration of one second with a 10-second pause between each level. Number sequence will vary between N-back conditions. The number of correct responses will be recorded to control for performance on the cognitive task itself. The repetitive visual stimulus activates the areas of the brain supplied by the PCA. A computer program will display a visual stimulus, as previously described. Briefly, the subject will be asked to focus their eves on a screen displaying an alternating black and white checkerboard stimulus for varied amounts of time (~40s each stimulus). The subject will be required to open and close their eyes when prompted by the research team.
- Post-testing blood sampling and urinalysis (visit 7 only). A urine sample and 4.0 Tablespoons of blood will be collected to repeat baseline blood measures (except for APOE genotype and B vitamins, which only need to be performed once).

VISITS 3 & 8: COGNITIVE FUNCTION (Virtual; 1.5 hour each)

Subjects will be instructed to refrain from taking over the counter medications for 48 hours, vigorous aerobic exercise and alcohol for 24 hours before testing. Subjects will be encouraged to eat a light meal or snack before coming to the lab.

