- Wechsler Visual Reproduction Test (I and II). This test assesses visuoconstructional and visual memory function. The subject will be presented with a series of complex line drawing and will be asked first to copy the drawing onto a piece of paper, then re-draw the picture from memory following a 20-minute delay. Drawings will be scored for accuracy and correct placement of picture elements. This test must be completed in-person, and will be administered during Neuronal Function visits #4 and #9.
- **NIH Toolbox** (This test must be completed in-person, and will be administered during Neuronal Function visits #4 and #9).
 - Attention. Attention will be measured by the NIH Toolbox Inhibitory Control and Attention Test. The Flanker task measures both a participant's attention and inhibitory control. The test requires the participant to focus on a given stimulus while inhibiting attention to stimuli (fish for ages 3-7 or arrows for ages 8-85) flanking it. Sometimes the middle stimulus is pointing in the same direction as the "flankers" (congruent) and sometimes in the opposite direction (incongruent). Scoring is based on a combination of accuracy and reaction time.
 - Episodic Memory. Episodic Memory refers to cognitive processes involved in the acquisition, storage and retrieval of new information and will be measured with the NIH Toolbox Picture Sequence Memory Test. The Picture Sequence Memory Test is a measure developed for the assessment of episodic memory. It involves recalling increasingly lengthy series of illustrated objects and activities that are presented in a particular order on the computer screen. The participants are asked to recall the sequence of pictures that is demonstrated over two learning trials; sequence length varies from 6-18 pictures, depending on age. Participants are given credit for each adjacent pair of pictures (i.e., if pictures in locations 7 and 8 and placed in that order and adjacent to each other anywhere such as slots 1 and 2 one point is awarded) they correctly place, up to the maximum value for the sequence, which is one less than the sequence length (if there are 18 pictures in the sequence, the maximum score is 17, because that is the number of adjacent pairs of pictures that exist).
 - Working Memory. Working Memory refers to a limited-capacity storage buffer that becomes

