 - Metal: The MRI scanner produces a constant strong magnetic field, which may cause any metal implants, clips, or implanted medical devices within your body to shift position or malfunction. You will not be allowed to participate in this study if you have any implanted metal, clips or devices. You will be screened to make sure that it is safe for you to enter a strong magnetic field. Please provide us with as much information as you can, for example if you had surgery in the past, so that we may decide whether it is safe for you to be a participant. Metallic objects brought into the MRI environment can become hazardous projectiles and can also interfere with the data quality. To minimize this risk, metal earrings, other piercings, necklaces and any other metal in contact with your body must be removed prior to the study. You must also remove all items from your pockets, including coins, electronics (including cell phones and hearing aids) and wallets. You must remove belts with metal buckles, and you may be asked to change into a gown that we will provide if your clothing contains significant metal, including metal underwire bras.
 - Inner ear damage: MRI scanning produces loud noises that can cause damage to the inner ear if appropriate hearing protection is not used. Earplugs and/or headphones will be provided to protect your ears.
 - Claustrophobia: When inside the MRI scanner, the "bore" of the scanner will surround the part of the body that is being scanned. In the case of fMRI, we are interested in brain activity, and the head will be centered inside a close-fitting scanning coil positioned in the bore of the scanner. If the subject feels anxious in confined, spaces they may not want to participate. If they are unsure, they can try the "mock" scanner at the MRI facility to evaluate their comfort level with the enclosed space of the magnet bore. If they decide to participate and begin to feel claustrophobic, they will be able to communicate with the research team via the intercom or the squeeze ball and the test will be discontinued.

Subjects who do not complete MRI testing will still be allowed to continue with the trial.

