To determine if pre-intervention differences exist between groups, subject characteristics (e.g. total body fat, fasting blood glucose, etc.) will be compared between the two groups using unpaired t-tests. If assumptions of normality are met, separate linear regression models will be fit to compare NR vs. placebo (independent variable) with respect to change (baseline vs. week 12) for each of the outcome variables. Linear regression methods will be used to determine the association between/among changes in the primary or secondary outcomes in response to NR supplementation (e.g., to examine the association between changes in cognitive function and changes in arterial stiffness or cerebrovascular function). If assumptions of normality are not met, alternative strategies will be used, including transformation of variables, generalized linear mixed models, and non-parametric regression. To account for the blocked randomization scheme, indicator variables for block assignment will be included in the model as appropriate. To account for multiple testing of primary outcomes of interest in response to treatment, a Hotelling's T test will be used. If this multivariate test is significant then individual outcomes will be compared between groups at an alpha level of 0.05. Secondary outcomes (brain blood flow and blood pressure/arterial stiffness) will be assessed similarly with an adjusted alpha level of 0.0125. All tertiary outcomes will be considered more exploratory for future hypothesis testing. Given the design, treatment conditions and assessment protocols, we anticipate missing data (due to subject dropout, missed data collections, etc.) to be at least missing at random (MAR), if not missing completely at random (MCAR). Based on my pilot study, we do not expect the assigned treatment condition (NR or placebo) to influence whether a subject opts to continue with the study. Assuming missing data that are MAR or MCAR, a linear model or generalized linear model would vield valid inference.

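### If the primary outcomes include all three named memory tests, the Hotelling's T gate drops anyone who misses one of two session pairs, and no missing-data rule covers that test

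*Combined protocol and SAP*

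**What the plan says.** **Gate.** Section 10 (How will data be analyzed and reported?) states: "To account for multiple testing of primary outcomes of interest in response to treatment, a Hotelling's T test will be used". It continues: "If this multivariate test is significant then individual outcomes will be compared between groups at an alpha level of 0.05". Without a significant gate, no primary outcome is compared individually.

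**Form of the outcomes.** The analysis variable is a change, so each score needs both time points: "separate linear regression models will be fit to compare NR vs. placebo (independent variable) with respect to change (baseline vs. week 12".

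**Primary domain.** Section 6 (Study Design) describes efficacy "for improving memory and other cognitive functions in adults with cognitive scores indicative of aMCI". The individual primary scores are not listed anywhere. Section 6 names three tests for memory: CVLT III, Wechsler Logical Memory and Wechsler Visual Reproduction.

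**Where the tests are given.** CVLT III and Logical Memory are described under the heading "VISITS 3 & 8: COGNITIVE FUNCTION (Virtual; 1.5 hour each". Visual Reproduction is placed elsewhere: "This test must be completed in-person, and will be administered during Neuronal Function visits #4 and #9". The NIH Toolbox carries the same restriction.

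**Partial completers.** Section 8 (MRI Scan) says: "Subjects who do not complete MRI testing will still be allowed to continue with the trial". Section 9 adds that a visit not completed at baseline is not scheduled at follow-up. Section 7 replaces participants who withdraw and says nothing of those who stay but miss a session.

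**Missing data.** Section 10 expects missed data collections and assumes they are MAR or MCAR. Its claim of valid inference reads: "Assuming missing data that are MAR or MCAR, a linear model or generalized linear model". It gives no imputation and no rule for an incomplete set of scores in the multivariate test.

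**The concern.** Hotelling's T compares two mean vectors, and a participant with a gap in the vector contributes nothing to the ordinary form of the test. The separate regressions need only the one score being analysed. If the primary scores span both session pairs, the test that decides whether anything primary is examined rests on fewer people than the tests it unlocks. Scores already collected from partial completers are left out at that step.

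Two things are at stake. The first is power at the gate: a failed gate ends the primary analysis. The second is coherence: the gate and the follow-up comparisons would describe different sets of participants. Also, if the data are MAR but not MCAR, a complete-case multivariate test is not protected by the argument that section 10 makes for its linear models.

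**Working it through.** **The plan's own figure.** Section 7 allows 25% on 58: 58 × 0.25 = 14.5, rounded to 15, and 58 + 15 = 73, as stated. The 58 itself cannot be reproduced, because no effect size, SD, power or sidedness is given. The effect, correlation and loss rates below are therefore assumptions.

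**Step 1: how many stay in the gate.** Section 9 links the two visits of a pair, because a missed baseline visit cancels its follow-up. The natural unit is therefore the pair (3/8 or 4/9). Let m be the assumed, independent probability of losing a pair.

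- Complete vectors: 58 × (1 − m)². At m = 5%: 58 × 0.9025 = 52.3, about 52. At m = 10%: 58 × 0.81 = 47.0.
- Available for any one score: 58 × (1 − m), about 55 and 52.
- At least one pair complete: 58 × (1 − m²), about 58 and 57.

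**Step 2: gate power.** Assume p = 3 tests, a true effect of 0.75 SD on each change score, pairwise correlation 0.5, and alpha 0.05.

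- Squared Mahalanobis distance: D² = d² × p / (1 + (p − 1)ρ) = 0.5625 × 3 / 2 = 0.844.
- Noncentrality: λ = (n₁n₂/N) × D², with F on p and N − p − 1 df.

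| Loss per pair | N in gate | n₁, n₂ | λ | df | Power |
|---|---|---|---|---|---|
| 0% | 58 | 29, 29 | 12.23 | 3, 54 | 82% |
| 5% | 52 | 26, 26 | 10.97 | 3, 48 | 77% |
| 10% | 47 | 23, 24 | 9.91 | 3, 43 | 71% |

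**Step 3: a different anchor.** If D² is instead set so that power is 80% at N = 58, three scores give 75% and 69% at losses of 5% and 10%. Twelve scores give 73% and 65%. The loss is similar in size and grows with the number of scores.

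**Step 4: what a joint model recovers.** The first two rows are simulations under the step 2 assumptions (1,500 runs, Monte Carlo SE about 1 point).

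| Losses | 5% per pair: complete-case vs joint | 10% per pair: complete-case vs joint |
|---|---|---|
| Both pairs | 79% vs 81% | 69% vs 78% |
| Visits 4/9 only | 81% vs 83% | 79% vs 83% |

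The gain is about 2 to 9 points. Joint values of 83% exceed the complete-data 82% only through simulation noise. With heavier losses the gain is larger. At about 19% per pair (1 − 0.9² = 0.19, leaving about 38 of 58), a separate simulation of 2,000 runs gave 58% vs 73%. These runs indicate the size of the gain from joint modelling; they do not validate the particular F test recommended below.

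**The case against.** **The primary scores are not listed.** If they all came from one session pair, for example CVLT III and Logical Memory at Visits 3/8, there would be no loss across pairs. This stands, and the point is conditional on it. The three tests that section 6 names for memory do span both pairs.

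**The plan never says complete cases.** That is true. But the ordinary Hotelling's T needs full vectors, and nothing else is specified for it.

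**Losses may be small.** CVLT III and Logical Memory can be done virtually. Section 6 (Study Timeline) lets sessions be reordered and moved by 7 days. Claustrophobia is an exclusion in section 7. The recruitment allowance includes experimental failure, so 58 may already be net of some failed sessions. All of this stands as mitigation. The allowance is pooled with dropout, failed screening and conversion to dementia, however, so it does not protect the number of complete vectors. None of these provisions says how the gate treats a gap.

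**A failed scan need not mean a failed memory test.** The section 8 sentence concerns the MRI. Visual Reproduction could still be given at that visit. Section 9 does allow the route to loss, since a participant who cannot go through with the baseline MRI is not scheduled for Visit 9. How often that would happen is unknown.

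**A stronger reading.** A reader might treat the four sessions as independent chances of loss, which at 5% and 10% per session would leave 47 and 38 of 58 and bring gate power to 71% and 60%. The documents do not support that model: section 9 ties each follow-up session to its baseline. Someone who leaves mid-trial loses Visits 8 and 9 together and falls under the replacement rule.

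**Conclusion.** The point holds conditionally. If the primary set spans Visits 3/8 and 4/9, the gate uses only participants with both pairs, and no missing-data rule in section 10 reaches it. At assumed losses of 5% or 10% per pair, 52 or 47 of 58 remain. Gate power falls from about 82% to about 77% or 71%, given 0.75 SD on each of three tests correlated 0.5. The documents supply none of these rates, the effect or the correlation.

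A reader might also infer that the gate result would be biased. The documents do not show this. Under MCAR the cost is power only. Under MAR bias is possible, but nothing in the plan allows it to be sized. Nor does a joint model restore full power, because it recovers only part of the loss. The change is worth making because it is cheap and uses data already collected.

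**What to change.** In section 10:

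1. List the primary scores and the visit at which each is obtained.
2. Compute the gate from one joint model of the primary change scores: one row per participant per test, unstructured covariance across tests, a treatment term for each test, and the same block or stratum indicators as the planned regressions.
3. Test all treatment terms jointly with an F test using a small-sample correction of Kenward-Roger type.
4. If the gate is significant, take the individual primary comparisons from the treatment terms of that same model. Only then do gate and follow-up tests use the same participants; separate single-score regressions would not.

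With complete data and no covariates this matches Hotelling's T. With gaps, each participant contributes the tests completed, and the plan's MAR reasoning extends to the gate.

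Cost: a few sentences, slightly more programming, and an approximate denominator df in place of the exact F. A short simulation of the chosen F test at the planned size would confirm its type I error before unblinding.

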Cognitive function assessments can be performed in-person during visit 3 and visit 8, or alternatively can be completed virtually through REDCap with research staff. If participants choose to complete cognitive testing through virtual means, visit 3 and visit 8 will no longer be needed.

Patient-Reported Outcomes (PROMIS) Measures (Visit 12). Subjects will answer a brief battery of selfguided questionnaires (administered using an iPad, or online via REDCap) to determine their own perception of their health and well-being. Outcome measures will include: fatigue, pain, physical function, sleep disturbance, anxiety, depression, alcohol use, and social abilities. Memory function will be assessed by performance on the **California Verbal Learning Test III (CVLT III)** and the **Wechsler Logical Memory and Visual Reproduction Tests.** Additional domains of cognitive function will be surveyed using the **NIH Toolbox** computerized tests to evaluate 1) attention, 2) episodic memory, 3) working memory, 4) language, 5) executive function, and 6) processing speed.

- CVLT III The subject will hear a list of 16 nouns in a fixed order over 5 learning trials. After each trial, the subject will be asked to recall as many words as they can in any order. Following the learning trials, the subject must recall as many words on the list as they can immediately (short-delay) and following a 20-minute wait (delayed recall). A second task involving recognition of target words from a list of 44-words read by the investigator is completed at the end of the test. This test can be performed in-person or virtually through REDCap and virtual screen sharing.
- Wechsler Logical Memory Test (I and II). This test assesses logical memory function. The subject will listen to the examiner read two stories and will be asked to repeat as many details of the stories as they can remember. An immediate recall and delayed (20 minute) recall component will be used. Scores will be based on accuracy in recalling elements of the story. This test can be performed inperson or virtually through REDCap and virtual screen sharing.

VISITS 4 & 9: NEURONAL FUNCTION (CBBI; 2 hours each)

Subjects will be instructed to refrain from taking over the counter medications for 48 hours, vigorous aerobic exercise and alcohol for 24 hours before testing. Subjects will be encouraged to eat a light meal or snack before coming to the lab.

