Repeat MRI Screening Form. To confirm ability to safely participate in the MR scan.

To gain initial insight into the possible central neural mechanisms mediating improvements in cognitive function with NR supplementation in older adults, we will use exploratory fMRI assessments of global and regional brain structure and task-induced neural activation patterns. As there is no preliminary evidence suggesting a change in activation patterns following NR supplementation in older adults, all fMRI-based outcomes are considered exploratory in nature and are not included as a primary/secondary outcome.

The scanning portion of the study will take

Table 2 **Outcome type** Assessment Task Structure Grey matter volume White matter volume White matter hyperintensities **Resting state** --Functional brain connectivity **Blood flow** Arterial spin labeling Cognitive N-Back Executive function activation Working memory

place at the UD Center for Biomedical Brain Working memory Imaging (CBBI). The MRI device for these scans is FDA approved for research with human subjects and has all the safety inherent in a clinical MRI scanner. The radio frequency fields conform to guidelines determined by the FDA and the FDA has designated MRI scanners to be a non-significant risk device. MR techniques non-invasively produce images and measurements from tissues in the intact, living human.

- Prior to going into the MRI scanner, the MRI technologist on duty will ask participants to remove all jewelry and metal objects from their pockets. Participants will be required to change into scrubs to prevent any possible risk from metallic objects or decorations in their clothing.
- In an MRI scan the subject will lay down on a table and will be placed into a long donut-shaped magnet. A specially designed coil will be placed around the head to provide better images (as is done with standard clinical examinations). As the MRI scan is performed, the subject will hear loud rapping and knocking noises that are normal for a MRI scan.
- The protocol will consist of an 8-min high-resolution structural scan to determine brain anatomy, a 6min scan of resting state activity to examine age-dependent functional brain connectivity, measurement of resting brain blood flow using arterial spin labeling (ASL) and a 10 minute cognitive

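### A significant Hotelling's T followed by unadjusted 0.05 tests does not hold familywise error at 5% when one primary outcome responds and two or more do not, and the primary outcomes are never named

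*Combined protocol and SAP*

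**What the plan says.** Section 10 (Data), under the question on how data will be analysed and reported, fits a separate linear model of 12-week change for each outcome. It then gives one multiplicity step for the primaries. The purpose is stated as "To account for multiple testing of primary outcomes of interest in response to treatment", the tool is Hotelling's T, and the follow-up rule is "If this multivariate test is significant then individual outcomes will be compared between groups at an alpha level of 0.05". No other section adds closed testing, Holm, an order of testing or any other step within the primary family. The alpha of the Hotelling test and the sidedness of the individual tests are not given.

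The primary outcomes are neither listed nor counted. Study Design in Section 6 gives the efficacy target as memory together with other cognitive functions. The text for Visits 3 and 8 names three memory tests (CVLT III, Wechsler Logical Memory, Wechsler Visual Reproduction) and adds NIH Toolbox domains. The memory tests have several components:

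- CVLT III has learning trials, short-delay recall, 20-minute recall and a recognition task.
- For Logical Memory, "An immediate recall and delayed (20 minute) recall component will be used".
- In Visual Reproduction the subject is "asked first to copy the drawing onto a piece of paper, then re-draw the picture from memory following a 20-minute delay".

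**The concern.** A significant multivariate test says that NR affects something in the family. It does not say which member. If a real effect on one outcome makes that test significant, every unaffected outcome is then tested at a full 0.05 with nothing to limit the total error across them.

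What is at stake is the claim most readers will want from this trial, namely which memory test or score improved. The plan presents the Hotelling step as its answer to multiple testing, but for that claim the protection is incomplete. Because the family is undefined, a reader of the plan cannot tell how incomplete.

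**Working it through.** The documents give no familywise error rate, effect size, SD or correlation, so there is no figure of the plan's to reproduce.

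**Step 1: where the rule is safe.**

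- *No outcome responds.* A false claim needs a significant Hotelling test, so the risk is at most 0.05.
- *At most one outcome is unaffected.* Only that outcome can yield a false claim, and its own test is at 0.05, so the risk is at most 0.05.
- *Two primaries.* These two cases cover every possibility, so two primaries are always protected.
- *Three primaries.* The only exposed case is exactly one responding.

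**Step 2: the ceiling where it is not safe.** If the overall test is almost certain to be significant and *m* independent outcomes are unaffected, the risk tends to 1 − 0.95^*m*:

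- *m* = 2 (three outcomes, one responding): 1 − 0.9025 = 9.75%
- *m* = 3 (four outcomes): 1 − 0.8574 = 14.3%
- *m* = 4 (five outcomes): 1 − 0.8145 = 18.5%

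**Step 3: simulation at this trial's size.**

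From the documents:
- 58 subjects (Section 7)
- two arms with near-equal blocked allocation (Section 6, Randomization), so 58/2 = 29 per arm
- individual alpha 0.05 (Section 10)

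Assumed:
- Hotelling test at 0.05 and two-sided t-tests on change
- normal data with equal correlation from 0 to 0.7
- the family sizes and effects shown
- 22 per arm as a sensitivity case: 58 × 0.75 = 43.5, about 22 in each arm

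A false claim is a significant Hotelling test plus at least one significant test on an unaffected outcome, in either direction.

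| Primary outcomes | Responding | Effect on responder(s) | Risk of a false claim |
|---|---|---|---|
| 2 | 1 | 0.3 to 2 SD | 3% to 5% |
| 3 | 0 | none | 3% to 5% |
| 3 | 1 | 0.3 SD | about 5% |
| 3 | 1 | 0.5 SD | 7% to 8% |
| 3 | 1 | 0.75 SD | 8% to 9% |
| 3 | 1 | 1 to 2 SD | 8% to 10% |
| 3 | 2 | 0.3 to 0.75 SD | 3% to 5% |
| 4 | 1 | 0.5 to 0.75 SD | 9% to 12% |
| 5 | 1 | 0.5 to 0.75 SD | 10% to 15% |

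With 22 per arm, three outcomes and one responder, the risk is 6% to 7% at 0.5 SD and 8% at 0.75 SD.

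**Step 4: why the risk climbs with the effect.** Take three uncorrelated outcomes with one responding:

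- At 0.5 SD the Hotelling test is significant in 30.7% of trials and the false-claim risk is 6.8%.
- At 0.8 SD the figures are 69.0% and 9.0%.
- At 1.2 SD they are 97.1% and 9.7%, close to the 9.75% ceiling.

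**Step 5: alternatives on the same settings.** Closed testing built from Hotelling tests and Holm both stay at or below 5%, within simulation error.

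**The case against.** The strongest case on the other side has four parts.

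- **The excess rests on assumptions.** Family size, effect, correlation and the alpha of the Hotelling test are not in the documents. With two primaries there is no fault. With three, exactly one must respond, by about 0.4 SD or more, before the excess is visible. This stands, and it limits the size of the problem but not its existence. The firm defect is that the family is unnamed, so the protection the plan describes cannot be checked.
- **A multivariate test before individual tests is a familiar convention, and no strong-control target is stated.** This is true. But the plan offers the step as its account of multiple testing and then invites claims on individual outcomes, and the step does not fully cover those claims.
- **It is tempting to say that 5% is assured only when NR affects nothing.** That is too broad. Control also holds whenever at most one outcome is unaffected: with two of three responding the simulated risk is 3% to 5%.
- **It is tempting to count two scores per memory test and take six as the family.** The documents do not say this. The tests do not divide evenly into two, and the copying step of Visual Reproduction is not recall. Three is no more certain, because the stated target also covers other cognitive functions.

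The risks above count errors in both directions. For uncorrelated outcomes, about half would favour NR.

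**Conclusion.** The concern holds in a bounded form. The rule does not hold familywise error at 5% when one primary outcome responds and two or more are unaffected. With three primaries and 29 per arm the excess is modest: 7% to 8% at 0.5 SD and at most about 10%. It grows with the number of unaffected outcomes. The mechanism is certain. The size depends on the assumptions listed, above all on how many outcomes are primary. It should be fixed, but it does not undermine the trial.

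Three things a reader might infer are not supported:

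- **That the headline result is inflated.** A claim that NR affects the primary family as a whole is still protected by the Hotelling test.
- **That the secondary rule is shown to be safe or unsafe.** The plan says "Secondary outcomes (brain blood flow and blood pressure/arterial stiffness) will be assessed similarly with an adjusted alpha level of 0.0125", but the number of secondary tests is not stated, so neither conclusion follows.
- **That the outcome tiers bear on this point.** Study Design says "Secondary outcomes will include measures of vascular/cerebrovascular and neuronal function and brain structure", while the Visits 4 and 9 text says "all fMRI-based outcomes are considered exploratory in nature and are not included as a primary/secondary outcome". That difference needs settling, but as a separate item.

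**What to change.** In the SAP, before unblinding, list the scores that enter the primary Hotelling test and state its alpha. Then, by the number named:

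- **Two:** no change.
- **Three:** keep Hotelling's T as a closed test. Claim an outcome only if its own test, both pairwise Hotelling tests that contain it and the three-outcome test are all significant at 0.05.
- **Four or more:** use Holm over the named scores at overall two-sided 0.05. Closed Hotelling testing is also valid at four or five and has more power when correlation is high. The number of subsets per score is 2^(*p* − 1): 8 with four scores, 16 with five, 32 with six.
- **If neither is wanted:** label the individual tests after the Hotelling test as descriptive and confine the confirmatory claim to the overall effect.

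This is a wording change and needs no new data. The cost is per-outcome power. With three outcomes at 0.5 to 0.75 SD and 29 per arm, closed testing loses about 1 to 3 points against the current rule when one outcome responds, 7 to 10 when two respond and 1 to 5 when all three respond.

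Holm's cost depends on correlation. With three outcomes and one responding at 0.75 SD, it is 4 points above the current rule at zero correlation and 14 below at 0.7. As a guide for larger families, take six scores with two responding at 0.75 SD: Holm has 56% to 57% power against 53% to 73% for the current rule. With four of six responding, it has 60% against 73% to 77%. The descriptive label costs no power but gives up confirmatory claims on single tests.
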